2.4 Defintion of other feasibility outcomes

2.4.1 Feasibility and acceptability of data collection tools: will be measured by proportion of patients randomised with complete patient-related outcome data at 3 months follow up.

The following proposed patient outcomes will be collected at baseline (pre-randomisation) and 3 months follow up (post randomisation)*:

- HRQoL: EuroQoL (EQ-5D-5L)
- Exercise/functional capacity: incremental shuttle walk test (ISWT);
- 4 Metre Gait Speed (MGS)
- Strength: Hand Grip Strength
- Mood: Patient Health Questionnaire-9 (PHQ-9);

PERFORM FEASIBILITY Protocol

Version 2.0 16.MAY.2023

- Generalised Anxiety Disorder Assessment-7 (GAD-7)
- Physical activity: International Physical Activity Questionnaire (IPAQ)
- Frailty: Functional Assessment of Chronic Illness Therapy; Fried Exhaustion and Weight Loss
- Fatigue (FACIT-F)
- Pain: Brief Pain Inventory (BPI)
- Health and disability: WHODAS
- Breathlessness: Dyspnoea-12
- Sleep: Medical Outcome Study Sleep Scale (MOS Sleep Scale)
- Cognition: MoCA
- Multimorbidity Treatment Burden Questionnaire (MTBQ)
- ICEpop CAPability Measures for Adults (ICECAP-A)
- Clinical events mortality & hospital admissions (& primary care contacts); and social and healthcare utilisation (including medication (assess at follow up only))

The following proposed patient outcome will only be collected at 3 months follow up (post randomisation)*:

Exercise adherence: Exercise Adherence Rating Scale (EARS)

*This list of patient outcomes will be finalised following stakeholder consultation that forms part of WP2 and any changes will be submitted as an ethics amendment.

2.4.2 Estimates of key cost drivers.

Details are provided in the economic evaluation section (section 9).

2.4.3 Risks of bias/contamination.

Any outcome assessor blind breaks will be recorded. Contamination will be assessed by asking control participants to report whether they knew anyone in the intervention arm of the trial and whether they had access to any intervention resources.

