6.6 Randomisation

The LCTU will supply a web based randomisation system from a third party (Sealed Envelope Ltd.). Participants will be individually randomised in a 2:1 ratio to intervention or control. Once the participant has provided written consent to the study and a healthcare professional has confirmed eligibility, randomisation will be performed randomly allocated in a 2:1 ratio to either PERFORM rehabilitation programme or standard of care. Randomisation will be minimised on site. To maintain concealment and minimise selection bias, randomisation will be performed after the baseline visit using a valuated password-protected web-based randomisation system supported by Leicester CTU to ensure concealment.

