6.8 Study Assessments

6.8.1 Baseline Assessments

- Inclusion/exclusion and study entry verification
- Demographics including:

Date of birth

Gender

Ethnicity

Marital/civil partnership status

Living situation

Smoking status

Employment status

Education status

Address (postcode)

Socio Economic Status

Caring responsibility

- Medical History (including Long term conditions,) Vital signs (height, weight, resting blood pressure, resting heart rate and respiratory frequency)
- Concomitant medicine check

Measures of physical capacity:

Exercise capacity

- Incremental shuttle walking test

The incremental shuttle walk test (ISWT; Singh et al., 1992 [50]) is an externally paced, incremental test that requires patients to walk around a 10m course at a speed dictated by an audio tape. The walking speed progressively increases each minute, for a maximum of 12 minutes, with the test terminated when the patient is no longer able to keep up with the target walking speed. Individuals will perform the ISWT twice pre-intervention for familiarisation purposes with the highest distance achieved used for exercise prescription, and once post-intervention.

Time to complete: 20 minutes

Physical frailty (as part of Fried; Fried et al., 2001 [51])

- 4 Metre Gait Speed (MGS)

The time (in seconds) taken to walk 4m at a usual pace will be recorded.

Time to complete: 2 minutes

Strength

- Hand Grip Strength (HGS)

Maximum handgrip strength will be measured using a dynamometer, performed three times on both the dominant and non-dominant hand. The highest score is taken per hand. This measure also part of the Fried frailty assessment (51).

Symptom burden:

Overall health

- EQ-5D-5L

The EQ-5D-5L (EuroQol Group, 1990 [52]) consists of the EQ-5D descriptive system and the EQ visual analogue scale (EQ VAS). The former has 5 dimensions (mobility, self-care, usual activities, pain/discomfort, and anxiety/depression) with 5 levels (no problems, slight problems, severe problems, extreme problems). The patient is asked to select an appropriate level for each dimension. The EQ VAS records the patient's self-rated health on a visual scale that ranges from 'the best health you can imagine' to 'the worst health you can imagine'.

Time to complete: 5 minutes

Fatigue

- FACIT

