6.13.1 Reporting Procedures for Serious Adverse Events

All SAEs related to the PERFORM study or rehabilitation programme (intervention) occurring from the time of written informed consent until the 3 month follow up visit must be reported to the Sponsor immediately and within 24 hours of becoming aware of the event. These related SAEs will be reported using appropriate forms and according to the Sponsor SOP for reporting serious adverse events. Additional information will be provided if requested to the Sponsor and main Research Ethics Committee (REC). The Principal Investigator or another delegated physician (as agreed by the Sponsor) is responsible for

the review and sign off of the SAE and the assessment of causality (i.e. whether an event is related to a study procedure or intervention).

If a delegated clinican from the reporting site is unavailable at the time of identification of a SAE the initial report without assessment of whether the event was related to the study or intervention should be submitted to the Sponsor. This must be completed immediately and within 24 hours of the study team becoming aware of the SAE, and must be followed-up by medical assessment as soon as possible thereafter.

The Sponsor will perform an initial check of the information and ensure that the SAE line listing is reviewed by the Director of Research & Innovation. All SAE information must be recorded on an SAE form and sent to the Sponsor. Additional information received for a case (follow-up or corrections to the original case) needs to be detailed on a new SAE form and sent to the Sponsor.

Copies of all documentation and correspondence relating to SAEs will be stored in the TMF and / or ISF

For each SAE the following information will be collected:

- a) full details in medical terms and case description
- b) event duration (start and end dates, if applicable)
- c) action taken
- d) outcome
- e) seriousness criteria
- f) relationship to the study procedure or intervention

Any change of condition or other follow-up information should be emailed to the Sponsor as soon as it is available or at least within 24 hours of the information becoming available. Events will be followed up until the event has resolved or a final outcome has been reached."

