10.6 Participant population

The analysis of the feasibility outcomes will be carried out in the ITT population.

Patient reported outcomes and clinical events will be analysed using the complete case population for the variable being summarised.

Adverse events will be analysed in the safety population, that all individual randomised with individuals receiving one or more session of the PERFORM intervention being analysed in the PERFORM intervention arm.

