10.7 Procedure(s) to account for missing or spurious data

Feasibility outcomes: For the feasibility outcomes relating to completeness of data there will be no need to account for missing data as this is exactly what the data is measuring fully completed or not (missing). Likewise, the number randomised will not need to account for missing data. For the proportion of sessions by patients in the PERFORM intervention arm, if the data for attendance at any session is truly missing and can be dissolved through data queries, individuals will be assumed to have not attend that session.

Patient outcomes/clinical events: sites will be asked to check completion of patient outcomes in order to mimimise any missing data. If items are missing from within an outcome questionnaire, the appropriate imputation method will be applied to allow outcome scoring. Data presentation for this feasibility study will consider completed outcomes and not impute any complete missing outcomes.

10.8 Other statistical considerations.

A statistical analysis plan will be finalised prior to final data lock and any deviations from the statistical plan will be reported in the statistical report.

[figure not shown]
Separate listings of SAEs will be presented as line listings; in addition to the description listing will include relatedness to intervention.

The number of serious adverse events will be presented overall and by randomised group. The number of patients with 0, 1, 2 etc events will be summarised overall and by randomised group.

The type and number (percentage) of protocol deviations will also be tabulated overall and by randomised group in the ITT population.

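### Baseline-test harms arise before randomisation, but adverse events are analysed only in randomised patients and SAEs are counted by arm with no onset limit (minor)

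*Protocol*

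**What the plan says.** Four parts of the Protocol bear on this point.

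- **Scope of harms.** Section 6.13 records adverse events related either to the rehabilitation programme or to study assessments. Under section 6.13.1, related SAEs "occurring from the time of written informed consent until the 3 month follow up visit must be reported to the Sponsor". No start date is given for non-serious related events, which go on an AE log and in the medical notes.
- **Timing of tests.** Section 6.8.1: "Individuals will perform the ISWT twice pre-intervention for familiarisation purposes with the highest distance achieved used for exercise prescription, and once post-intervention". The same section describes a practice and a repeat walk and plans the baseline assessments for one visit. Section 2.4.1 says that patient outcomes "will be collected at baseline (pre-randomisation) and 3 months follow up (post randomisation", and section 6.6 says that "randomisation will be performed after the baseline visit".
- **Analysis population.** Section 10.6: "Adverse events will be analysed in the safety population, that all individual randomised". Patients who receive at least one session are placed in the intervention arm.
- **Tabulation.** Section 10.8: "The number of serious adverse events will be presented overall and by randomised group". It also promises SAE line listings, for which no population is stated. The only relatedness item it names for them is relatedness to the intervention.

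**The concern.** The window for reporting harm opens at consent, but the population for analysing harm begins at randomisation. The baseline visit, with its two incremental walk tests, lies between the two. Two things follow if the text is applied literally.

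1. A consented patient harmed in a baseline test, and for that reason not randomised, is outside the only population named for adverse-event analysis. Whether the event is counted then depends on the event itself, because a worse event makes randomisation less likely.
2. A patient with a baseline-test event who is later randomised has that event counted in an arm, although it happened before allocation.

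The study aims to judge whether its methods are fit for the full trial (section 2.1.1), and study assessments are one of only two sources of recordable harm. Section 6.9 says that exercise risk is highest with pre-existing cardiovascular disease. Section 5.1 admits patients with coronary heart disease and heart failure. Section 6.3 says that severity, exclusions apart, does not influence screening. How safe the baseline tests are is therefore something the main trial would want to learn from this study.

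**Working it through.** The Protocol states no figure for this point, so there is nothing to reproduce. The check sets the stated rules in time order and then asks what can be sized.

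**Order of events.** Consent (SAE reporting opens, 6.13.1) → baseline visit with two shuttle walks (6.8.1) → randomisation (6.6) → programme or usual care → 3-month visit with one shuttle walk (6.8.1, 6.8.3). The analysed population (10.6) is formed at the third step. The SAE counts (10.8) have no onset rule.

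**Consequence 1: patients left out.** Let k be the number consented and tested but not randomised. The number randomised is 60 (section 10.1). The share of tested patients outside the safety population is k / (60 + k). The Protocol does not give k, so these values are assumptions:

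| k (assumed) | Tested | Share outside |
|---|---|---|
| 0 | 60 | 0% |
| 3 | 63 | 3/63 = 4.8% |
| 6 | 66 | 6/66 = 9.1% |
| 12 | 72 | 12/72 = 16.7% |

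These are shares of patients tested, not of events. The Protocol gives no event rate from which to derive the latter.

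**Consequence 2: events placed in an arm.** With 40 and 20 patients (section 10.1), let E be the number of pre-randomisation events in patients who are later randomised. The expected split is E × 40/60 = 2E/3 in the intervention arm and E × 20/60 = E/3 in control. Expected rates per patient are (2E/3)/40 = E/60 and (E/3)/20 = E/60, which are equal. Raw counts are therefore expected to run 2:1 towards the intervention arm, while rates show no systematic difference. A single such event still adds 1/40 = 2.5 percentage points to the intervention arm, or 1/20 = 5 points to control, and neither reflects allocated treatment.

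**Context: where the shuttle walks fall.** In 60 randomised patients there are 60 × 2 = 120 walks before randomisation. Afterwards there are 60 with no loss, or 60 × 0.8 = 48 at the 20% loss anticipated in section 10.1. The pre-randomisation share is 120/180 = 66.7% to 120/168 = 71.4%. This shows only that most of this testing comes before allocation. All 120 of those walks are in patients inside the safety population.

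**The case against.** The best reply has five parts.

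- **The events remain visible.** Related SAEs go to the Sponsor within 24 hours (6.13.1). They are also reviewed by the Programme Steering Committee (6.13), which considers progression to the full trial. The line listings in 10.8 carry no population limit, so such an SAE might appear there. This stands, and it rules out the tempting reading that baseline-test harms disappear from oversight. It does not supply a tabulated count or a denominator. It also does not cover non-serious related events, for which 10.8 promises no listing.
- **A randomised-only safety set is normal.** This stands for comparing arms, and that set should be kept for the purpose. It does not suit harms that arise before allocation.
- **The SAP may split events by onset.** It may; it is not at hand. That would settle the second consequence. The first rests on a population that the Protocol itself fixes.
- **The 67% to 71% share measures nothing lost.** Correct. A reader might infer that about two-thirds of test-related harm goes unanalysed. The documents do not support this, since those walks belong to randomised patients.
- **Few events are likely.** Section 6.9 calls the risk of harm with exercise very low, and harms are not among the progression criteria in section 2.2. This stands and keeps the point minor.

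**Conclusion.** The point holds as a minor one. The Protocol opens SAE reporting at consent, counts harms from assessments, and does both baseline walks before randomisation. It then analyses adverse events only in randomised patients and counts SAEs by arm with no onset limit. A baseline-test harm that prevents randomisation is therefore outside the analysed and tabulated harms, most clearly when it is non-serious. A baseline-test event in a patient who is later randomised is placed in an arm that could not have caused it.

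The size of the first effect is unknown. It is 0% of tested patients if k = 0 and 4.8% to 16.7% over the assumed range k = 3 to 12. A reader might infer from the 2:1 allocation that the second effect biases the comparison against the intervention. It does not bias rates per patient, whose expected values are equal. It is misattribution and noise in a study of 40 and 20 patients.

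**What to change.** In sections 10.6 and 10.8:

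1. Keep the randomised safety population for the by-arm harms table, but restrict that table to events with onset after randomisation.
2. Add a separate summary of assessment-related AEs and SAEs from consent to randomisation. The denominator should be all consented participants who began a baseline assessment, whether or not they were later randomised.

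In section 6.13, state that the AE log also starts at consent, so that non-serious events are captured over the same window as SAEs.

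The cost is a few sentences, one extra table column and a count of participants assessed at baseline. Section 10.2.1 does not list that count for the CONSORT diagram. Related SAEs are already reportable from consent, but sites would need to be told when the AE log starts. The by-arm totals would no longer include events from before allocation.

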3. TRIAL DESIGN

A parallel two group randomised feasibility study with nested process and economic evaluation. Patients will be randomly allocated to either intervention (PERFORM rehabilitation programme + usual care) or control (usual care alone). The feasibility study will be conducted across four sites with a total of 60 participants recruited over a 4.5 month period, with 40 participants randomised to the intervention group and 20 participants to the control group with a 3 month follow up after randomisation and a further 2 group maintenance sessions at 4 and 6 month post randomisation.

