6.13 Recording and reporting of SAEs Definitions

| Term | Definition |
|------|------------|
| | |

Adverse Event (AE)

Any untoward medical occurrence in a patient or clinical investigation participants, which does not necessarily have to have a causal relationship with this treatment.

An AE can therefore be any unfavourable and unintended sign (including an abnormal laboratory finding), symptom or disease temporally associated with the the study, whether or not considered related to the study.

For this study, only those deemed related to the PERFORM rehabilitation programme (intervention) or study assessments will be documented on an AE log and in the patient's medical notes.

Adverse Reaction (AR)

An untoward and unintended response in a participant to an investigational medicinal product which is related to any dose administered to that participant.

The phrase "response to an investigational medicinal product" means that a causal relationship between a trial medication and an AE is at least a reasonable possibility, i.e. the relationship cannot be ruled out.

All cases judged by either the reporting medically qualified professional or the Sponsor as having a reasonable suspected causal relationship to the trial medication qualify as adverse reactions. It is important to note that this is entirely separate to the known side effects listed in the SmPC. It is specifically a temporal relationship between taking the drug, the half-life, and the time of the event or any valid alternative etiology that would explain the event.

For this study, only those deemed related to the PERFORM rehabilitation programme (intervention) or study assessments will be documented on an AE log and in the patient's medical notes

Serious Adverse Event (SAE)

A serious adverse event is any untoward medical occurrence

- results in death
- is life-threatening
- requires inpatient hospitalisation or prolongation of existing hospitalisation
- results in persistent or significant disability/incapacity
- consists of a congenital anomaly or birth defect

Other 'important medical events' may also be considered serious if they jeopardise the participant or require an intervention to prevent one of the above consequences.

NOTE: The term "life-threatening" in the definition of "serious" refers to an event in which the participant was at risk of death at the time of the event; it does not refer to an event which hypothetically might have caused death if it were more severe.

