7. INTERVENTION & CONTROL

7.1 Intervention group

The PERFORM rehabilitation programme will comprise an 8 week supervised rehabilitation programme, 6 weeks, twice weekly then 2 weeks, once a week that will be offered in either a primary or secondary care setting. Each session will last for 2 hours (1hr of 'move and improve

exercise sessions, and 1hr patient 'Health and Wellbeing' self care support session and Q&A/opportunity to interact with the group). The intervention will be offered within 4 weeks of randomisation.

The rehabilitation programme will comprise an exercise component with an accompanying education programme. The 'Health and Wellbeing' self care support sessions / educational package will offer advice and support for behaviour change to support positive lifestyle changes and symptom management. Much of the advice will be appropriate to all participants for example health eating, the benefits of exercise, stress management and relaxation techniques, medicines adherence, and exacerbation of symptoms. The aim of the education 'health and wellbeing' package is to support symptom management, risk factor management and enhance self-management skills. The education programme will be delivered by healthcare professionals delivered as informal and interactive sessions. The information will be supplemented by written leaflets and material to support the individual to share with their family and carers. After the 8 week programme the participant will have a discharge appointment in most cases this will take place 1-2 weeks following the last rehabilitation session.

Each 'move and improve' exercise session will offer an individually prescribed and progressed aerobic walking programme (a combination of walking (treadmill where available). In addition resistance training will be delivered that will be individually prescribed and progressed.

Participants will also be encouraged to complete a home exercise programme that will be closely monitored. A home exercise booklet will be provided as well as a progress tracker standardised exercise diary that will ask participants to record exercise frequency, duration and symptom scores post bout of exercise. This will be recorded for the aerobic and resistance programme.

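### Adverse events are grouped by sessions received but serious adverse events by randomised group, so one event can be counted in different arms

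*Protocol*

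**What the plan says.** Section 10.6 of the protocol defines the set for harms: "Adverse events will be analysed in the safety population, that all individual randomised". It then assigns the arm by receipt, with "individuals receiving one or more session of the PERFORM intervention being analysed in the PERFORM intervention arm".

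Section 10.8 uses another rule for the serious subset: "The number of serious adverse events will be presented overall and by randomised group". The next sentence applies the same rule to patients: "The number of patients with 0, 1, 2 etc events will be summarised overall and by randomised group".

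Four other statements bear on the point:

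- **Section 3** plans the trial "with 40 participants randomised to the intervention group and 20 participants to the control group".
- **Section 7.1** allows a gap before the programme starts: "The intervention will be offered within 4 weeks of randomisation".
- **Section 6.13.1** requires reporting of related SAEs "occurring from the time of written informed consent until the 3 month follow up visit", a window that includes time before, and without, any session.
- **Section 6.13** limits what is recorded: "only those deemed related to the PERFORM rehabilitation programme (intervention) or study assessments will be documented on an AE log". The SAE entries in the same table carry the same limit.

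**The concern.** SAEs are a subset of AEs, so both rules govern the same events. They agree only if every intervention patient attends at least one session and no control patient attends any. Otherwise an SAE can count towards one arm in the AE table and the other arm in the SAE table, over different denominators. A reader of the feasibility report, or the Programme Steering Committee in its data monitoring role, could not tell which count is the intended one.

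A second point follows from 10.6 alone. The safety population is everyone randomised, and the stated condition for the PERFORM arm is at least one session. An intervention patient with no session does not meet that condition, and no arm is named for that patient. If such patients are added to the usual-care side, that group is no longer the randomised control group. The event itself may be the reason for not starting: a patient hurt in baseline testing, then allocated to PERFORM and unable to begin, would be moved because of the event being counted.

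**Working it through.** **Text side by side**

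| | AEs (10.6) | SAEs and patients by event count (10.8) |
|---|---|---|
| Arm set by | at least one PERFORM session | randomised group |
| Intervention patient, no session | not in the PERFORM arm on the plain reading; destination not stated | intervention |
| Control patient who attended a session | PERFORM | control |

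The last two rows are where the rules part. No sentence says that both displays are intended.

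**Inputs**

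- Planned arms (section 3; 2:1 allocation in section 6.6): 60 × 2/3 = 40 and 60 × 1/3 = 20. The protocol's 40/20 is reproduced.
- Number of intervention patients with no session, *m*: not given. Section 8 foresees such patients, since it plans to interview people who did not attend. The values of *m* below are assumptions.
- Control patients attending a session: not given; set to zero here. Each one would move the by-receipt split by one the other way.

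**Denominators by receipt**, if patients with no session are counted with control: PERFORM = 40 − *m*; comparator = 20 + *m*; share of the comparator that was randomised to PERFORM = *m* / (20 + *m*).

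| Assumed share with no session | *m* | PERFORM / comparator | Share of comparator randomised to PERFORM |
|---|---|---|---|
| 5% | 2 | 38 / 22 | 2/22 = 9% |
| 10% | 4 | 36 / 24 | 4/24 = 17% |
| 20% | 8 | 32 / 28 | 8/28 = 29% |
| 30% | 12 | 28 / 32 | 12/32 = 38% |
| 40% | 16 | 24 / 36 | 16/36 = 44% |

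By randomised group, the arms stay 40/20 in every row.

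**One illustration with assumed events.** Suppose four patients randomised to PERFORM have a recorded event, one of them is among *m* = 4 with no session, and no control patient has an event.

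- By randomised group: 4/40 = 10.0% against 0/20 = 0%.
- By receipt: 3/36 = 8.3% against 1/24 = 4.2%.

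**Which events can move.** Sections 6.13 and 6.13.1 admit only events related to the programme or to study assessments. A patient who attended no session can hardly have a programme-related event, which leaves assessment-related ones. Section 6.8.1 has two shuttle walk tests at baseline and one after the intervention, section 6.6 places randomisation after the baseline visit, and section 6.13 itself anticipates musculoskeletal injury from the programme and assessments. So the events that can change arm are mainly injuries in the baseline or 3-month tests among non-starters, and events in control patients who attended a session.

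**The case against.** A reader might infer that the by-receipt rule makes the programme look safer: patients who fall ill during the wait of up to 4 weeks never start, and their events pass to control. The documents do not support that. Intercurrent illness unrelated to the programme or assessments is neither logged as an AE nor reported as an SAE, and the schedule in section 6.1 shows no assessment between baseline and the programme. The wait therefore adds almost no recordable harm, and its length as a share of follow-up does not measure the problem. The steering committee description does mention a summary of all SAEs, but section 6.13 restricts reporting to related ones.

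Four further points count against a strong reading.

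- Deaths and hospital admissions are collected as clinical events (section 2.4.1) and summarised by randomised group (section 10.2.3), so a non-starter's admission or death, where recorded, is counted in the randomised arm there.
- SAEs are also line-listed with relatedness, so no reported SAE disappears.
- That non-starters become controls is implied and not stated. The sentence could be meant only for control patients who gain access to the programme.
- An as-treated safety set is a legitimate choice, and detail may be left to the statistical analysis plan.

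These points remove the bias argument and most of the size. They do not remove the conflict. Sections 10.6 and 10.8 each fix a rule, the rules differ for the same events, and even the lenient reading of 10.6 leaves the place of patients with no session unstated.

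**Conclusion.** The inconsistency is real and of low severity. AEs are grouped by receipt and SAEs by randomisation, with nothing to reconcile them, so an event in a non-starter or in a control patient who attended a session can be counted in different arms.

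The size cannot be fixed from the protocol, because the number of non-starters is not given. The shifts to 36/24 and 32/28 rest on an assumed 4 or 8 of 40 and on reading 10.6 as placing these patients with control. The event counts in the illustration are also assumed. Because only related events are recorded, few events are likely to be affected, although with 20 controls a single one is visible.

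The progression criteria rest on recruitment, retention and attendance, and section 10.5 sets no formal stopping rule. The decision on a full trial therefore does not depend on this point.

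**What to change.** Amend sections 10.6 and 10.8 so that one grouping governs both AE and SAE tables. Randomised group is the natural choice, since 10.8 and 10.2.3 already use it. Then:

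- State that intervention patients with no session stay in their randomised arm and are not added to control.
- State likewise that control patients who attended a session stay in control in the main tables.
- If a by-receipt display is wanted, show it only as a supportive table, labelled as such and with its own denominators.

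The statistical analysis plan should carry the same wording. The cost is a few sentences and at most one small table, with no new data collection.
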